## **10 ADVERSE EVENT REPORTING**

### **10.1 Adverse Events**

Reporting of adverse events will comply with federal regulations for IDE safety reporting. AEs occurring during the enrollment period should be documented by the Investigator in progress notes but will not

be collected or analyzed by Indiana University School of Medicine unless considered serious and research related by the Investigator. The MedDRA scale will be used to describe adverse events.

Serious adverse events (SAEs) related to the research treatment that are encountered during study enrollment will be documented by the Investigator and reported to Indiana University School of Medicine within 72 hours upon discovery. SAEs are defined under current cGCP guidelines as events that result in one or more of the following:

- life-threatening illness or injury;
- permanent impairment of a body structure or a body function;
- medically necessary in-patient hospitalization;
- medical or surgical intervention necessary to prevent permanent impairment to body structure or function; or
- fetal distress, fetal death, or congenital abnormality.

Serious events that affect the rights, safety, or welfare of subjects must be documented on a form and be reported within 72 hours to Indiana University School of Medicine and to the Investigator's IRB according to that IRB's policies.

Any potential deficiencies with the BioCue™ devices (including, but not limited to deficiencies in packaging, labelling, and/or device processing) will be reported to Zimmer Biomet for evaluation.

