**SYNOPSIS**

Title of Study	Safety and efficacy of concentrated autologous concentrated bone marrow aspirate (BMAC) in preventing wound complications in amputations
Objectives	

• Determine the safety and explore efficacy of BMAC in preventing wound complications in amputations.

• Characterize the host tissue response to, paracrine activity of, and fate of transplanted BMAC.

• Determine the effects of chronic limb ischemia and diabetes on nerve function and to assess the effects of mesenchymal stem cell administration on their function.

Planned Number of Subjects and Duration of Involvement	12 patients, 12 month follow up period
Patient Population	Critical limb ischemia (CLI) patients scheduled for amputation
Investigational Product Name	Concentrated autologous bone marrow aspirate (BMAC)
Methodology Overview	
This is an open label pilot trial.
 
Up to twelve (12) patients scheduled for amputation will receive bone marrow cells concentrated (BMAC) via the BioCue™ Platelet Concentration Kit device injected IM at 25 sites in the leg proximal to the amputation in the index limb to prevent ischemic wound complications after surgery. BMAC will be injected into the anterior tibialis muscle (ATM) below the point of amputation for analytical purposes. Patients will be scheduled for amputation at Day 7 post injection. Safety will be evaluated by review of treatment related adverse events (AE) during the 12-month follow-up period. In subjects undergoing BKA, we will compare rates of wound complications and conversion from BKA to AKA to historical controls at our institution to assess trends in therapeutic efficacy.
 
Patients will undergo amputation and injection sites will be harvested from the ATM at that time. Immunohistochemical staining (IHC) will determine capillary density and local host immune responses. Angiogenic and inflammatory cytokines will be quantified using a multiplex array system and quantitative polymerase chain reaction (PCR).

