#### **6.1.2 Safety issues**

Safety of the BioCue™ device to concentrate BMA for the prevention of wound complications in amputation will be determined by review of treatment related adverse events (AE) and serious adverse events (SAE) during the study period of 12 months by the Data Safety Monitoring Board (DMSB) appointed by the Clinical and Translational Sciences Institute (CTSI) at the Indiana School of Medicine or Data Safety Committee (DMC) designated by the Principal Investigator.

The BMAC dose proposed in this trial was selected based on prior clinical trials. We may not see any evidence of efficacy in our composite endpoint, which may reflect an inadequate dose or sample size. In this case we would propose a future study exploring escalating doses of BMAC. In the instance of evolving infection, we would re-assess our inclusion/exclusion criteria and evaluate the contribution of pre-amputation procedures on the lower leg. Patients may request earlier amputation due to worsening rest pain or anxiety. Consideration for amputation sooner than one week post injections will be determined by the PI based on the severity of the subject's condition, so as to offer this research as an option to all eligible subjects.

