### **9.3 Planned Analyses**

The clinical study report will contain only summary data analyses reflecting safety profiles, and summary data analyses of efficacy. All patient data will remain coded during analyses to maintain patient confidentiality.

The data management center for this trial will be at the CTSI, or a Data Monitoring Committee (DMC) will be appointed by the Principal Investigator. We will use a web-based HIPAA compliant online system for data entry and data management, as we are currently doing in our current clinical trials. Data will be collected from each enrolled patient using a comprehensive case report form and uploaded into a specifically designed database in the OnCore Enterprise Clinical Trial Management System and VA REDCap system. All the data will be analyzed and generated using SAS.

**Safety Assessment.** Primary attention will focus on the safety of the administration of BMAC as measured by treatment-related AEs. Treatment-related AEs will be categorized overlapping systems and severities. Three categories of systems are cardiovascular, respiratory, or infectious. Two categories of severity will be serious adverse (SAE) and major adverse cardiac events (MACE). For completeness, instances of AEs may appear in more than one category. Within each of these categories AEs will be listed in descending order of frequency for the treatment group. In addition, for each category, the sum and difference between the two routes of delivery of the proportions will be reported as percent incidence. Binomial confidence Intervals at the 95% confidence level and *p*-values for these 3 groups will be calculated. Since previous trials have not reported AEs with BMAC treatment, confidence intervals will be generated by the method of the Wilson Score Interval because they are robust, with good coverage probability even for small number of trials and are not degenerate near zero. These intervals will be used to summarize the data rather than as any formal inferential statement and to assist the Data Monitoring Board in their deliberations. No adjustment for multiplicity will be made.

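### Section 10.1 leaves non-serious treatment-related AEs uncollected, although Section 9.3 makes treatment-related AEs the main safety measure; AE evaluation is also last scheduled at Week 24 of a 12-month safety window

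*Combined protocol and SAP*

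**What the plan says.** **Collection rule.** Section 10.1 has the investigator note AEs of the enrollment period in progress notes. It then says they will not "be collected or analyzed by Indiana University School of Medicine unless considered serious and research related by the Investigator". Both conditions, serious and related, must be met.

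**Analysis.** Section 9.3 states: "Primary attention will focus on the safety of the administration of BMAC as measured by treatment-related AEs". It sorts these events by system ("Three categories of systems are cardiovascular, respiratory, or infectious") and by two severity labels, SAE and MACE, and reports proportions category by category with Wilson intervals.

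**Review and window.** Section 6.1.2 says that safety "will be determined by review of treatment related adverse events (AE) and serious adverse events (SAE) during the study period of 12 months", naming AEs and SAEs separately. The Synopsis has: "Safety will be evaluated by review of treatment related adverse events (AE) during the 12-month follow-up period". Sections 3 and 7.1 say the same.

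**Schedule.** The AE/SAE row of Table 4 is marked at Visits 2 to 9, from BMAC injection to Week 24, and is blank at the Week 52 call. Only the infection/gangrene row and the amputation-revision row are marked at that call. Section 7.1 says the call is for primary endpoints, a term the documents do not define.

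**The concern.** Both passages already restrict to related events, so they differ on seriousness alone. A non-serious, treatment-related AE belongs to the analysis in 9.3 and is shut out by the collection rule in 10.1. The two cannot both be followed.

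Safety is part of the first objective, and 9.3 prepares for counts near zero. It introduces the choice of interval method with the words "Since previous trials have not reported AEs with BMAC treatment". A zero or low count could then reflect good tolerability or the collection rule, and the intervals meant to help the monitoring board cannot tell the two apart.

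A second, smaller question is whether AEs are actively sought over the whole of the stated 12 months.

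**Working it through.** The plan gives no AE rate or other figure to reproduce. The check is a comparison of passages, with a little arithmetic for scale.

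**1. Which events fall between the two rules**

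| Event | In the 9.3 safety measure? | Collected under 10.1? |
|---|---|---|
| Serious, related | yes | yes |
| Non-serious, related | yes | no |
| Not related | no | not under the AE rule |

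The second row is the conflict. The support for reading 9.3 as covering non-serious events is its wording on treatment-related AEs, its system categories (which carry no seriousness condition) and the separate naming of AEs and SAEs in 6.1.2. The severity labels give no such support, because neither SAE nor MACE is a non-serious category.

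**2. What is lost within the named categories**

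- Wound infection is recorded in any case under Section 7.1.
- The loss due to 10.1 is therefore mainly non-serious related cardiovascular and respiratory events, and infectious events other than wound infection.
- Rash, myalgia, pain and bleeding, all named as risks in Section 11.1, are lost twice: 10.1 does not collect them when non-serious, and they match none of the three system categories.

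**3. Illustrative size in one category**

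Inputs: n = 12 (Section 5.1.1), z = 1.96, Wilson interval (Section 9.3).

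Limits = [p + z²/(2n) ± z·√(p(1−p)/n + z²/(4n²))] / (1 + z²/n)

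- z² = 3.8415, so z²/(2n) = 0.1601, z²/(4n²) = 0.00667 and 1 + z²/n = 1.3201.
- x = 1: p = 0.0833. Centre = (0.0833 + 0.1601)/1.3201 = 0.1844. Half-width = 1.96 × √(0.00637 + 0.00667)/1.3201 = 0.1695. Interval 1.5 to 35.4%.
- x = 0: centre = 0.1601/1.3201 = 0.1212, and the half-width is the same. Interval 0 to 24.2%.

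One subject whose only event in a category is related but non-serious would move that category from the first result to the second. The denominator does not change, so the bias runs one way.

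**4. Time without a scheduled AE/SAE evaluation**

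52 − 24 = 28 weeks. With the ±2-week window at Week 24, the range is 52 − 26 = 26 to 52 − 22 = 30 weeks. This is calendar time, not a share of risk or of expected events.

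**5. Reach of the enrollment-period qualifier**

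The term is undefined. Read as a subject's time on study, the rule covers all follow-up. Read as accrual, it covers about 3 years (Section 5.2.2) against 52 weeks of follow-up per patient (Section 4.2). AEs after accrual closes would escape it, but those before would not. The conflict is then narrower in time but remains.

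**The case against.** **Other text points to wider collection.** Section 9.3 says: "Data will be collected from each enrolled patient using a comprehensive case report form". Table 4 schedules AE/SAE evaluation at eight visits. A reader might infer that 10.1 is contradicted by both, or overridden by them. Neither follows. The case-report-form sentence does not name AEs, and a progress note could satisfy a scheduled evaluation. They suggest an intention to collect more but do not cancel an explicit exclusion.

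**The size may be overread.** A reader might infer from step 3 that the overall AE proportion is misstated by 1/12. Section 9.3 defines no overall any-AE proportion, so the figures apply only within a named category. Nor can the loss of rash or myalgia be laid on 10.1 alone, since 9.3 has no category for them even with full collection. The intervals are described as summaries rather than formal inference, and no stated decision rule uses them. All of this stands and limits the size, but descriptive counts still need complete numerators.

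**Other reporting routes exist.** Sterility failures are reported as AEs (Section 6.1.3), wound infection and stump revision are recorded (Section 7.1), and serious events affecting subjects' rights, safety or welfare go on a form with no relatedness condition (Section 10.1). These narrow the gap. None covers non-serious related AEs in general.

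**Week 52 is not empty.** A reader might infer that safety is not followed after Week 24. That goes too far: the call covers infection, gangrene and revision, its undefined primary endpoints may include AEs, and related SAEs are reportable on discovery. What is missing is a marked AE/SAE evaluation.

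**Conclusion.** The inconsistency is real and must be fixed. As written, 10.1 removes non-serious treatment-related AEs from the safety summary that 9.3, 6.1.2, the Synopsis and Sections 3 and 7.1 promise, and this can only lower the reported proportions. The number of events affected cannot be computed from the documents; the 1/12 versus 0/12 comparison is only an illustration of scale for a single category. The conclusion assumes that the enrollment period means time on study; under an accrual reading it holds for a shorter period.

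The Week 24 point is secondary. It is a mismatch between a 12-month window and the marked schedule, not proof that late events are missed.

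A reader might also infer that every AE must be collected whatever its cause. The documents promise only treatment-related AEs, so reconciling them does not require that.

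**What to change.** - **Section 10.1.** Require that at least all treatment-related and possibly related AEs, serious or not, from the start of the marrow harvest/BMAC procedure to the end of the safety window, are entered on the CRF with seriousness, relatedness and CTCAE grade. CTCAE is the scale named in Section 7.3.2; reconcile this with the reference to a MedDRA scale in 10.1. Define the enrollment period. Collecting all AEs regardless of relatedness is optional.
- **Section 9.3.** Add an other-system category and a row for any treatment-related AE.
- **Window.** Add AE/SAE evaluation to the existing Week 52 call and define primary endpoints. Alternatively, restate the safety window as Week 24 in the Synopsis and Sections 3, 6.1.2 and 7.1. The second option is cheaper but gives up the 12-month safety statement.
- **Subjects already treated.** The Introduction says some were treated under prior protocol versions, and the documents do not show which collection rule then applied. Where their non-serious related AEs were not collected, abstract them from progress notes and flag them as retrospective.

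**Cost.** A protocol amendment, AE pages for at most 12 subjects and one item on an existing call, with no extra visit. The downsides are modest data entry, retrospective data that are less complete, and an AE table that looks less favourable.

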## **11** RISK ANALYSIS

### **11.1** Potential Risks of the Investigational Product and Clinical Investigation

The types of risk associated with IM injection are notably rash, mild fever, and myalgia. These risks are mild and rare. These risks are all stated in the consent form.

Further risks include pain, bleeding, and infection following the surgical procedure. Additionally, as with any other surgical procedure, the investigational device may be dropped in the surgical theater. Flash sterilization will not be allowed, and additional sterile devices will be available to prevent procedure termination with minimal delay.

### **11.2** Potential Benefits of the Investigational Product and Clinical Investigation

Subjects are not expected to benefit in any way from their participation in the study.

The studies made possible by the data collected in this study are expected to lead to the prevention of wound complications after major amputation.

### **11.3 Minimization of Risks**

Although the risk to subjects participating in the study is anticipated to be minimal, the clinician, at his/her discretion, will not collect data from those individuals for whom collection is judged to pose an unusually high risk of physical or mental harm or discomfort.

An additional risk is the event that a syringe containing the bone marrow product or the centrifugation tube is dropped. In this case the syringe or tube would be recovered, swabbed externally with alcohol, the needle/cap removed and replaced with a sterile needle, and then the sterile contents containing the bone marrow product will be emitted into a sterile container on the sterile surgical field and reloaded into a new sterile 10 cc syringe and needle. The dropped syringe will be discarded and not contact the sterile field(s). In the rare event that the investigator feels that the bone marrow product comes into contact with the non-sterile environment then the bone marrow product will be discarded, which is a total volume of 6 mL of the planned 30 mL to be injected. Additional bone marrow will not be aspirated and the patient will receive 25 mL rather than 30 mL of bone marrow product. It must be emphasized that the sterile field encompasses the area of the patient's limb continuous by sterile drapes to the operating room table where the bone marrow product is loaded into syringes, thus the likelihood of the syringe contacting a non-sterile surface is minimal. Likewise, the centrifugation tube is a closed sterile system with fixed caps and should it fall to the floor the contents would remain in the closed sterile system and recovered as described.

Participation in this study poses no risk to study personnel other than that normally encountered during standard practice. These risks will be minimized by adherence to the following guidelines:

- Personnel should wear appropriate personal protective equipment to avoid contact of the eyes or skin with hazardous materials or products derived from biological sources.

## **12 INVESTIGATOR RESPONSIBILITIES**

### **12.1 Site Qualification and Study Oversight**

The PI is responsible for general administration of the study.

Before the study, the PI must:

- Obtain approval to conduct the study from the study site's IRB;
- Sign the Protocol Signature Page themselves and have all sub-investigators sign the Protocol Signature Page and return it to Indiana University School of Medicine;
- Provide financial disclosures to Indiana University School of Medicine for themselves and all sub-investigators participating in study conduct, per Title 21CFR 54 (see **Section 12.4** below).

During the study, the PI must ensure that:

- The study is conducted ethically;
- Case report forms (CRFs), including Subject ICFs, are provided with each transfer of data requiring informed consent; and
- All other study forms are completed as instructed by Indiana University School of Medicine.
- Investigators, primary care physicians, and all enrolled diabetic subjects follow the American Diabetes Association guidelines for diabetic care throughout the trial.

In the case of completion or termination of the study or an Investigator's role in the study, or at Indiana University School of Medicine request, all study materials must be returned to Indiana University School of Medicine.

## **12.2 Case Report Forms/Electronic Data Records**

As used in this protocol, the term CRF should be understood to refer to either a paper form or an electronic data record or both, depending on the data collection method(s) used.

Original CRFs are the sole property of Indiana University School of Medicine and should not be made available in any form to third parties, except for authorized representatives of Indiana University School of Medicine or appropriate regulatory authorities, without written permission from Indiana University School of Medicine.

It is the PI's responsibility to ensure completion, review, and approval of all CRFs. CRFs must be signed by the PI or by an authorized staff member. These signatures serve to attest that the information contained on the CRFs is true. At all times, the PI has final personal responsibility for the accuracy and authenticity of all clinical and laboratory data entered on the CRFs.

## **12.3 Access to Source Documents**

Indiana University School of Medicine or its agents and appropriate regulatory authorities shall be granted direct access to all study-related documents to perform verification that the protocol and all applicable current cGLPs, GCPs, and regulations are being followed and to confirm that study documents are complete and accurate. It is important that Investigator(s) and their relevant personnel be made available during monitoring visits and any audits or inspections, and that sufficient time is allotted for the process.

## **12.4 Financial Disclosure**

Investigators must provide Indiana University School of Medicine with sufficient, accurate financial information in accordance with local regulations to allow Indiana University School of Medicine to submit complete and accurate financial certification or disclosure statements to the appropriate health authorities. Investigators are responsible for providing information to Indiana University School of Medicine concerning their relevant financial interests during the course of the study and for 1 year after completion of the study. Conflicts of interest should be disclosed as required by law.

## **12.5 Deviations from the Study Protocol**

An Investigator may not deviate from the study protocol without prior approval by Indiana University School of Medicine unless the deviations are necessary under emergency circumstances to protect the rights, safety, or well-being of human subjects or the scientific integrity of the clinical investigation. These deviations must be documented and promptly reported to Indiana University School of Medicine and, if applicable, to the IRB providing oversight of the study. Protocol deviations may result in corrective and preventive actions and/or disqualification of the Investigator. If research blood draws (Research Blood Specimen) are not obtained at time points specified in the schedule of events, they will not be considered protocol deviations.

## **12.6 Record Retention**

To enable evaluations and/or audits from regulatory authorities or Indiana University School of Medicine, the PI and all sub-investigators agrees to retain all study records, including copies of all CRFs, UADE forms, and source documents, for 3 years following completion of the project dependent upon

the study data. The Investigator must obtain the Indiana University School of Medicine written permission before disposing of any records, even if retention requirements have been met.

If an Investigator relocates, retires, or for any other reason withdraws from the trial, Indiana University School of Medicine must be notified in advance, and study records must be transferred to a designee acceptable to Indiana University School of Medicine. This designee might be another Investigator, another institution, or Indiana University School of Medicine itself.

